6.2.2 Karolinska Sleepiness Scale

The KSS is a 9-item, self-reported subjective measure of a subject's level of drowsiness ([Åkerstedt and Gillberg 1990](#)). Respondents must choose the statement that most accurately describes their level of sleepiness over the past few minutes. The KSS will be administered on the handheld device.

The morning assessment on the handheld device should be done at least 1 hour after the dose of study drug is taken in the morning.

6.2.3 Trail Making Tests

The TMT is a neuropsychological test of visual attention and task switching ([Reitan 1958](#)). The TMT has two parts, Parts A and B. Part A measures rote memory and consists of 25 circles on a piece of paper with the numbers 1-25 written randomly in the circles. The subject is to connect the circles in numerical order. Part B measures executive functioning and consists of 24 circles on a piece of paper, half of the circles have the numbers 1-12 in

them and the other half (12) contain the letters A-L. The subject must alternate connecting circles with numbers and circles with letters.

This clinician-administered assessment is to be completed at the clinic visits indicated in [Table S-1](#).

6.2.4 Hopkins Verbal Learning Test - Revised

The HVLT is a brief verbal learning and memory test with six alternate forms ([Brandt 1991](#)). The HVLT is ideal in situations calling for repeated neuropsychological examinations, but it lacks a delayed recall trial which is essential for the assessment of abnormal forgetting and therefore the revised version of the HVLT (HVLT-R) was developed. The HVLT-R test consists of three trials of free-recall of a 12-item, semantically categorized list, followed by yes/no recognition. Approximately 20-25 min later, a delayed recall trial and a recognition trial are completed.

This clinician-administered assessment is to be completed at the clinic visits indicated in [Table S-1](#).

6.2.5 Parkinson's Disease Non-motor Symptoms Questionnaire

The NMS questionnaire is a validated, clinician-rated questionnaire that assesses non-motor issues that may be present in Parkinsons disease ([Chaudhuri et al. 2006](#)). The PD NMS is comprised of 30 items grouped into nine domains: digestive, urinary tract, apathy/attention/memory, hallucinations/delusions, depression/anxiety, sexual function, cardiovascular, sleep disorders, and miscellaneous.

This clinician-administered assessment is to be completed at the clinic visits indicated in [Table S-1](#).

6.2.6 Patient Global Impression - Improvement

The PGI-I is a global index used to rate the response of a condition to a therapy. It is a simple, direct, easy to use scale that is intuitively understandable to subjects and clinicians. The PGI-I asks the patient to rate their symptoms now, as compared with how it was at Baseline before beginning treatment, ranging from 1=very much better to 7=very much worse.

Severity ratings should be based on the behavioral symptom(s) of clinical concern used for eligibility.

This assessment is to be completed at the clinic visits indicated in [Table S-1](#).

6.2.7 Clinical Global Impression - Improvement

The CGI-I is a clinician-rated, 7-point scale that is designed to rate the improvement in the subject's non-motor neuropsychiatric symptoms at the time of assessment, relative to the symptoms at Baseline ([Guy 1976](#)).

Severity ratings should be based on the neuropsychiatric symptom(s) of clinical concern used for eligibility.

This clinician-administered assessment is to be completed at the clinic visits indicated in [Table S-1](#).

6.2.8 Subject and Informant Satisfaction Question

Subject and informant will be assessed as to the satisfaction of the treatment the subject is getting during the study. The general question, "How satisfied are you with the treatment [you are] / [subject is] getting?" will be asked to the subject and separately to the informant. Answers will be rated on a scale of one (lowest, not satisfied) to five (highest, very satisfied).

This assessment is to be completed on the handheld device.

6.2.9 Actigraphy

An actigraph is a non-invasive instrument to assess cycles of activity and rest, and will be used in this study as a method to monitor rest/activity cycles of participants. An actigraphy instrument worn on the wrist will record movements and physiological measures to estimate activity parameters including daily activity, gait, and sleep parameters.

6.3 Safety Assessments

6.3.1 Physical Examinations

A physical examination including neurological exam (cranial nerves, motor, sensory, reflexes, gait, and coordination) will be conducted.

6.3.2 Vital Signs

Vital signs will include body temperature, resting respiration rate, systolic and diastolic blood pressure, and pulse rate.

Each time vital signs are measured the following procedures for orthostatic blood pressure (BP) and pulse rate (PR) evaluation should be followed:

- After the subject is supine for approximately 5 minutes, BP and PR will be measured and the subject will then be instructed to rise to a standing position if able. Then BP and PR will again be measured 1-3 minutes after standing. A drop in systolic BP of ≥ 20 mm Hg, or in diastolic BP of ≥ 10 mm Hg, within 3 minutes of standing, or experiencing

significant lightheadedness or dizziness after standing, along with a remarkable drop in BP as judged by the Investigator with agreement of the Sponsor's Medical Monitor, is considered orthostatic hypotension. Patients who have orthostatic hypotension at Screening (Visit 1) or Baseline (Visit 2) are not eligible for the study.

6.3.3 Height, Weight, and Body Mass Index

Height will be reported in centimeters or inches.

Weight will be reported in kilograms or pounds.

BMI will be calculated using the following formula: $Weight (kg) / [height (m)]^2$.

6.3.4 Electrocardiograms

All 12-lead ECGs will be complete, standardized recordings. All ECGs will be centrally read; the interpretation by the central cardiologist is considered the official interpretation. The ECG will be completed in triplicate at Visit 1 (Screening) and will be collected within an approximately 5-minute period. A single ECG tracing is to be completed at all other designated visits.

The following conditions apply:

- If a site performs additional ECGs beyond the set of triplicate ECGs prescribed at Screening or the single ECG prescribed at Baseline, the mean QTcF/QRS values of all the tracings of adequate quality will be used to determine eligibility. Values from tracings of inadequate quality will not be included in calculating the mean.
- If the mean QTcF value from the set of ECGs done at Screening is prolonged due to an identifiable cause, and it is medically appropriate to address that cause, a repeat set of triplicate ECGs may be performed during Screening at the discretion of the Medical Monitor. In this case, the repeat set of triplicate ECGs will be used in determination of subject eligibility.
- At Baseline, a subject may be enrolled based on the machine read of the locally completed ECG. If the interpretation of the ECG by the central cardiologist indicates QTcF outside of the allowable range, the subject will be discontinued from the study, but enrollment of the subject will not be considered a protocol deviation.

The subject must rest in a supine position for at least 3 minutes before the ECG is obtained. ECG tracings (paper or electronic) will be reviewed and interpreted by a qualified clinician. ECG tracings and results (ventricular rate, PR, QRS, QT, QTcF and QTcB intervals) will be included and summarized in the subjects study records.

6.3.5 Movement Disorders Society-Unified Parkinson's Disease Rating Scale

The MDS-UPDRS is a comprehensive battery of motor and behavioral indices derived from the Columbia Scale (Fahn et al. 1987). The MDS-UPDRS Part III will be used to assess motor function and is a motor examination consisting of 18 rater-based items. Only Part III will be administered during the study.

The MDS-UPDRS assessments should be conducted in the “on” state. This will ensure that noise associated with a subject’s “on/off” status does not confound interpretation of the motor function data.

This is a clinician-administered assessment and is to be completed at the clinic visits indicated in [Table S-1](#).

6.3.6 Columbia-Suicide Severity Rating Scale

The C-SSRS monitors changes in suicidal thinking and behavior over time, in order to determine risk (Posner et al. 2011). The following four constructs are measured: the severity of ideation, the intensity of ideation, behavior, and lethality.

The C-SSRS will be used to assess suicidal ideations and behaviors. The Baseline/Screening version will be administered at Visit 1 (Screening), and the “Since Last Visit” version will be administered at all other designated visits. The C-SSRS results for each subject should be reviewed by the Investigator at each visit. If at any time the C-SSRS results for a given subject reveal potential suicidality, then the Investigator should assess the clinical significance of such results. If a clinically significant risk of suicidality is identified for a subject, then the Investigator should discontinue the subject and implement appropriate treatment ([Section 4.4](#)).

This is a clinician-administered assessment and is to be completed at all clinic visits.

6.3.7 Laboratory Evaluations

Clinical laboratory sample collection (including HbA1c at Screening only) is encouraged, but not required, to be completed under fasting conditions. The laboratory evaluations will include, but are not limited to, the following:

- Clinical chemistry serum tests
 - Sodium (Na), potassium (K), chloride (Cl), phosphorus (P), calcium (Ca), magnesium (Mg), carbon dioxide (CO₂), blood urea nitrogen (BUN), creatinine (CR), uric acid
 - Mg should only be performed at Visit 1 (Screening)

- Alanine aminotransferase (ALT), aspartate aminotransferase (AST), gamma-glutamyl transpeptidase (GGT), alkaline phosphatase (ALP), total bilirubin (TBIL), lactate dehydrogenase (LDH)
- Vitamin B12
 - Vitamin B12 should only be performed at Visit 1 (Screening)
- HbA1c
 - HbA1c should only be performed at Visit 1 (Screening)
- Glucose
- Albumin (ALB), total protein
- Prolactin (Week 4/EOT will be blinded, also performed at Baseline)
- Thyroid stimulating hormone (TSH) and reflex free T4, if TSH is out of range
 - TSH/free T4 should only be performed at Visit 1 (Screening)
- Creatine kinase (CK)/creatine phosphokinase (CPK)
- Insulin (at Baseline and Week 4 only)
- Lipid panel
 - Total cholesterol, HDL-cholesterol, triglycerides, LDL-cholesterol, cholesterol/HDL ratio, non-HDL cholesterol, very low density lipoprotein cholesterol
- Pregnancy test
 - A serum pregnancy test should only be performed at Visit 1 ([Table 6-1](#)) for women of childbearing potential
 - A urine pregnancy test should be performed at all designated visits after Visit 1 ([Table 6-1](#)) for women of child-bearing potential
 - If urine cannot be obtained in women of childbearing potential, a serum pregnancy test should be done
- Hematology tests
 - Complete blood count (CBC) including:
 - White blood cell (WBC) count
 - Absolute neutrophil count
 - Complete differential (relative and absolute)

- Hematocrit (Hct), hemoglobin, red blood cells (RBC), platelets
- Reticulocyte count
- Urinalysis
 - Blood, RBCs, WBCs, protein, glucose, ketones, specific gravity, pH
 - Reasonable efforts should be made to collect a urine sample from all subjects. Where collection of a urine sample proves impractical or impossible (e.g., because the subject is incontinent), failure to collect a urine sample should be recorded in the subject's case report form (CRF), and will not be considered a protocol deviation
- Urine toxicity screen
 - The following controlled substances may be tested with a urine toxicity screen according to the schedule presented in [Table 6–1](#): amphetamine, barbiturates, benzodiazepines, cocaine, methadone, morphine/opiates, methamphetamine, marijuana (THC), phencyclidine (PCP), ecstasy (MDMA).
 - Subjects who test positive for benzodiazepines, THC, or opiates may continue in the study and last usage should be noted at the study visit. In addition, restrictions listed in [Appendix A](#) should be followed.
 - Reasonable efforts should be made to collect a urine sample (as described in “Urinalysis” above) at all designated visits

Laboratory evaluations will be completed according to the schedule presented in Table 6–1 and procedures detailed in the study Manual of Procedures. Additional safety testing may be performed at the discretion of the Investigator or designee. All laboratory results should be evaluated for clinical significance and be reported as an AE/SAE, as applicable.

Table 6–1 Safety Laboratory Evaluations

Visit	Tests ^{a,b}
Visit 1 (Screening, Week -4)	CHEM, CBC, UA, urine toxicity screen, and serum pregnancy test
Visit 2 (Baseline, Week 0)	CHEM, CBC, UA, insulin, prolactin, urine toxicity screen, and urine pregnancy test
Visit 4 (Week 2)	CHEM, CBC, and UA
Visit 6/ET (Week 4/EOT)	CHEM, CBC, UA, insulin, prolactin (blinded), urine toxicity screen, and urine pregnancy test

Abbreviations: CBC=complete blood count; CHEM=clinical chemistry serum tests; EOT=end of treatment; ET=early termination; TSH=thyroid stimulating hormone; UA=urinalysis

^a A pregnancy test is only required for women of childbearing potential. If urine cannot be obtained in women of childbearing potential, a serum pregnancy test should be done.

^b A vitamin B12 test, HbA1c, Mg level, and TSH/free T4 test are only required at Visit 1 (Screening).

6.4 Safety Follow-up

A 30-day safety follow-up telephone contact is to be completed for subjects who complete the treatment period of the study as well as those who discontinue prematurely from the study. Subjects should have the following completed 30 (± 4) days after last dose of study drug:

- Assessment of concomitant medications/treatments
- Assessment of AEs

6.5 Unscheduled Visits

Unscheduled visits may occur as determined by the Investigator and may include any safety evaluations deemed by the Investigator to be clinically indicated. The following safety assessments will typically be performed; however, these are neither required nor all those that may be performed: assessment of AEs, assessment of concomitant medications/treatments, measurement of vital signs, study drug accountability, and completion of the C-SSRS.

7 ADVERSE EVENTS

7.1 Specification of Safety Parameters

7.1.1 Definition of Adverse Event

An AE is defined as “any untoward medical occurrence in a patient or clinical study participant, temporally associated with the use of study drug, whether or not considered related to study drug”.

An AE can therefore be any unfavorable and unintended sign (e.g., an abnormal laboratory finding), symptom, or disease temporally associated with the use of a drug, without any judgment about causality or seriousness. An AE can arise from any use of the drug (e.g., off-label use, use in combination with another drug) and from any route of administration, formulation, or dose, including an overdose.

A suspected adverse reaction is any AE for which there is a reasonable possibility that the drug caused the AE.

AEs do not include the following:

- Stable or intermittent chronic conditions (such as myopia requiring eyeglasses) that are present prior to Baseline and do not worsen during the study
- Medical or surgical procedures (e.g., surgery, endoscopy, tooth extraction, transfusion). The condition that leads to the procedure is an AE if not present at Baseline.
- Overdose of concomitant medication without any signs or symptoms unless the subject is hospitalized for observation
- Hospitalization for elective surgery planned prior to study (situation where an untoward medical occurrence has not occurred)
- Pregnancy will not be considered an AE, but if it occurs, it will be reported on a pregnancy form

7.1.2 Definition of Serious Adverse Event

In addition to the severity rating, each AE will be classified by the Investigator as “serious” or “not serious.” The seriousness of an event will be defined according to the applicable regulations and generally refers to the outcome of an event. An SAE is one that meets one or more of the following:

- Is fatal
- Is immediately life threatening
- Results in disability or permanent damage
- Requires hospitalization
- Prolongs existing hospitalization
- Is a congenital anomaly or birth defect (in an offspring)
- Is medically significant

Definition of Life Threatening

A life-threatening event places the subject at immediate risk of death from the event as it occurred. This does not include an AE, which, had it occurred in a more severe form, might have caused death.

Definition of Hospitalization

Hospitalization is defined by the Sponsor as a full admission to the hospital for diagnosis and treatment. This includes prolongation of an existing inpatient hospitalization.

Examples of visits to a hospital facility that do **not** meet the serious criteria for hospitalization include:

- Emergency room visits (that do not result in a full hospital admission)
- Outpatient surgery
- Preplanned or elective procedures
- Protocol procedures
- Social hospitalization, defined as admission to the hospital as a result of inadequate family support or care at the subject's primary residence

Definition of Disability or Permanent Damage

Disability is defined as a persistent or significant incapacity or substantial disruption of the ability to conduct normal life functions.

Definition of Medically Significant

Important medical events (medically significant events) that may not result in death, be life threatening, or require hospitalization may be considered to be an SAE when, based upon appropriate medical judgment, they may jeopardize the subject or may require medical or surgical intervention to prevent one of the outcomes listed in this definition. Examples of such events are intensive treatment in an emergency room or at home for allergic bronchospasm, blood dyscrasias, or convulsions that do not result in hospitalization or development of drug dependency or drug abuse.

An SAE may also include any other event that the Investigator or Medical Monitor judges to be serious or that suggests a significant hazard, contraindication, side effect, or precaution.

7.2 Classification of an Adverse Event

7.2.1 Severity of Event

The severity of each AE will be graded on a 3-point scale and reported in detail as indicated on the eCRF:

- **Mild:** awareness of sign or symptom but easily tolerated, causing minimal discomfort, and not interfering with normal everyday activities
- **Moderate:** sufficiently discomforting to interfere with normal everyday activities
- **Severe:** incapacitating and/or preventing normal everyday activities

7.2.2 Relationship to Study Drug

The causality of each AE should be assessed and classified by the Investigator as “related” or “not related.” An event is considered related if there is a reasonable possibility that the event may have been caused by the product under investigation (i.e., there are facts, evidence, or arguments to suggest possible causation).

Consider the following when assessing causality:

- Temporal associations between the agent and the event
- Response to cessation (de-challenge) or re-challenge
- Compatibility with known class effect
- Known effects of concomitant medications
- Pre-existing risk factors
- A plausible mechanism
- Concurrent illnesses

7.2.2.1 Duration

The start and stop dates for AEs will be recorded using the following criteria:

- **Start:** Date of the first episode of the AE or date of significant sustained worsening in severity
- **Stop:** Date when AE either ceased permanently or changed in severity

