6.1.4 Medical History and Demographics

A complete medical history will be obtained from each potential subject. Demographic information, including date of birth, gender, race, and ethnicity will be recorded as well. Any new medical condition beginning after the informed consent form (ICF) has been signed will be captured as an AE. Subjects may be asked to provide pharmacy or medical records to substantiate the medication history.

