7.2.2.2 Frequency

The frequency of the AE should be indicated according to the following definitions:

- **Single:** Experienced once, without recurrence
- **Recurrent:** More than one discrete episode with the same severity

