7.3 Time Period and Frequency for Event Assessment and Follow-up

Adverse events will be recorded from the time informed consent is obtained through the safety follow-up period. All AEs must be either resolved or stable at the end of the safety follow-up period. If ongoing at the end of the safety follow-up period, the subject should be referred for appropriate treatment.

In the event that a subject discontinues and has an ongoing AE at the time of discontinuation (Section 4.4.1) or is withdrawn from the study because of an AE, the subject should be

followed and treated by the Investigator until the AE has resolved, stabilized, or a new chronic baseline has been established.

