14.1 Adverse Events

The primary endpoint for this study is treatment-emergent adverse events (TEAEs). Adverse events will be coded using MedDRA dictionary, Version 23.0.

An AE (classified by preferred term) will be considered a treatment-emergent AE (TEAE) if started after first study dose administration and no later than last study dose date + 30. AEs reported on Day 1 based on Baseline (pre-dose) findings (e.g., clinically significantly abnormal vital signs, laboratory test results, or electrocardiogram parameters) will not be considered as TEAEs.

The number and percentage of subjects reporting TEAEs in each treatment group will be tabulated by system organ class (SOC) and preferred term; by SOC, preferred term, and maximum severity; and by SOC, preferred term, and relationship to study drug. If more than 1 AE occurs with the same preferred term for the same subject, then the subject will be counted only once for that preferred term using the most severe and most related occurrence for the summarization by severity and by relationship to study drug.

The relationship of selected AEs to COVID-19 will be assessed as detailed in the GSD. COVID-19 related adverse events will be listed separately.

TEAEs will also be tabulated by treatment group and without displaying the SOC terms; this table will be sorted in descending order of frequency of preferred term within the pimavanserin group.

The incidence of most frequently reported (preferred terms reported by 2 or more subjects) TEAEs, treatment emergent SAEs, and TEAEs leading to discontinuation of study drug will be summarized by SOC, preferred term, and treatment group. The tables will be sorted alphabetically by SOC and then by descending frequency within each SOC. In addition, the incidence of fatal treatment-emergent AEs (i.e., events that cause death) will be summarized separately by preferred term and treatment group.

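### An AE open at first dose that becomes more frequent on study drug at unchanged severity keeps its Screening start date and is not counted as a TEAE

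*Protocol*

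**What the plan says.** - **Collection window (Protocol 7.3):** "Adverse events will be recorded from the time informed consent is obtained through the safety follow-up period". Section 6.1.4 agrees: "Any new medical condition beginning after the informed consent form (ICF) has been signed will be captured as an AE". Screening lasts 7-28 days (3.1), so an AE record can exist before any dose.
- **Start date (Protocol 7.2.2.1):** "Date of the first episode of the AE or date of significant sustained worsening in severity".
- **Stop date (Protocol 7.2.2.1):** "Date when AE either ceased permanently or changed in severity".
- **Frequency (Protocol 7.2.2.2):** an AE is either single or recurrent. Recurrent means "More than one discrete episode with the same severity". No number or rate of episodes is defined.
- **What is not an AE (Protocol 7.1.1):** "Stable or intermittent chronic conditions (such as myopia requiring eyeglasses) that are present prior to Baseline and do not worsen during the study". Worsening is not limited to severity here.
- **TEAE, protocol (9.5.1):** an AE that occurs after the first dose and up to 30 days after the last.
- **TEAE, SAP (14.1):** an AE is a "treatment-emergent AE (TEAE) if started after first study dose administration" and no later than 30 days after the last dose. There is no clause for a pre-dose AE that worsens.

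SAP 14.1 names TEAEs as the primary endpoint. SAP 19, on changes from the protocol, mentions only the move from repeated-measures models to ANCOVA.

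**The concern.** The start rule has one trigger for re-dating an existing AE, which is worse severity. A rise in frequency is not a trigger. The SAP then decides treatment emergence by the start date alone. An AE that was occasional before dosing and frequent afterwards, at the same grade, is therefore classed with the pre-treatment events.

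This matters because TEAE incidence is the primary endpoint and tolerability is part of the primary objective. Protocol 1.4 links daytime sedation on quetiapine with dizziness and a greater risk of falls, and such events can come as discrete episodes. If an event of this kind led to withdrawal, it would also be absent from the table of TEAEs leading to discontinuation, since that table is a subset of TEAEs.

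The two documents also use different tests (occurrence against start), and Protocol 7.1.1 and 7.2.2.1 treat worsening differently. The classification of such an event depends on which sentence the programmer follows.

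**Working it through.** The plan gives no figure to reproduce. The check is a trace of the dating rules into the SAP definition, followed by the weight of one subject.

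**Trace, for a condition first present before dosing**

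| Case | Dating under Protocol 7.1.1 and 7.2.2 | TEAE under SAP 14.1? |
|---|---|---|
| (a) AE recorded in Screening, still open at first dose, more frequent on drug, same severity | One recurrent record, Screening start | No |
| (b) As (a), but with significant, sustained worsening in severity | New start date on drug | Yes |
| (c) Resolved and closed before dosing, then returns | A new record is possible | Yes, if so entered |
| (d) Start date missing or incomplete, order unclear | SAP 5.6 assigns it to treatment | Yes |
| (e) Chronic intermittent condition, not an AE until it worsens (7.1.1) | Can first be recorded on drug | Yes, if dated at the worsening |

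Only case (a) is lost with certainty. The loss needs the start rule, the recurrent label and the SAP's start test together; no one of them is enough. If Protocol 9.5.1 were read literally, the on-drug episodes in case (a) could count, so for this case the protocol and SAP can give opposite answers.

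**Weight of one missed subject** = 1/n in the arm.
- Planned: up to 60 subjects at 1:1:1, so n = 60/3 = 20 and 1/20 = 5 percentage points.
- Actual: 11 randomized (SAP 19). The split is not given. If it was 4, 4 and 3 (assumed), 1/4 = 25 points and 1/3 = 33 points.

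**Illustration only.** No episode rate is in the documents. Assume 0.1 episodes per week in Screening and on placebo, 0.3 on quetiapine, exponential (gamma, shape 1) variation between subjects, and T = 4 treatment weeks. Assume also that every Screening episode is an AE that stays open and that none changes severity. With S weeks of Screening and on-treatment rate r:

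P(counted under the rule) = 1/(1 + 0.1S) − 1/(1 + 0.1S + rT).

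For S = 4: quetiapine 1/1.4 − 1/2.6 = 0.714 − 0.385 = 33%; placebo 1/1.4 − 1/1.8 = 0.714 − 0.556 = 16%; difference 17 points. Counting subjects whose weekly rate rose above their Screening rate (which includes new events) gives, by numerical integration, 45% v 19%, a difference of 26 points. The share of the difference lost is about 35% at 4 weeks of Screening, 29% at 3, 17% at 2 and 4% at 1. These are upper-end figures, because the last assumption closes routes (b) to (e). They show how the loss depends on Screening length and are not an estimate for this trial.

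**The case against.** The strongest reply is that few events would fall through:

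- **Severity can absorb frequency.** Protocol 7.2.1 grades an event as moderate when it is "sufficiently discomforting to interfere with normal everyday activities". Repeated episodes may reach that threshold and so earn a new start date. This stands where the worsening is also judged significant and sustained. It does not help an event that stays mild.
- **Records can close.** A single, resolved Screening event can be closed and a later one entered afresh; nothing in 7.2.2.2 says that separate resolved events must be merged. This stands, and it limits the problem to records still open at first dose.
- **Other safeguards exist.** SAP 5.6 counts AEs of unclear onset as treatment-emergent, and SAP 14.1 lists Screening events with their frequency. Neither cures case (a): the start date there is complete, and the defined frequency values are only single or recurrent, so no change in rate can be read from the listing.
- **The consequence is modest.** TEAEs are summarised descriptively in an unpowered pilot, the study has stopped, and 11 subjects can be reviewed individually. This stands as to scale. The tables still report the primary endpoint, and the pilot is meant to guide later studies.

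A reader might infer more than the documents support. They do not show that such events are never counted (cases b to e), nor that the subject drops out of all TEAE tables, since SAP 14.1 counts by preferred term and system organ class and other TEAEs still appear. They do not say that sedation, dizziness or falls on quetiapine typically show up as more frequent mild episodes. An event severe enough to force withdrawal would often be graded above mild, and SAP 6 tabulates discontinuation reasons separately. Finally, the stop rule closes a record on any change in severity while only worsening opens one. That is untidy, but no planned analysis uses AE duration, so it does not affect the endpoint.

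**Conclusion.** The point holds in a limited form. An AE recorded in Screening, open at first dose, and more frequent on drug at unchanged severity is not a TEAE under SAP 14.1 and cannot appear among TEAEs leading to discontinuation. The protocol's definition could be read the other way, and the SAP does not record the difference as a change.

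The number of such events cannot be derived from the documents. Each affected subject with no other TEAE in the category concerned moves that arm's incidence by 5 points at the planned 20 per arm, or by 25 to 33 points on an assumed 4, 4, 3 split of the 11 randomized. The direction of any effect on the comparison with placebo depends on episode rates that are not given. If a drug raises frequency without raising severity, the difference from placebo would shrink.

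**What to change.** 1. **Use one TEAE definition** in Protocol 9.5.1 and SAP 14.1: an AE that started, or that worsened in severity or frequency relative to its pre-dose state, after the first dose and up to 30 days after the last dose.
2. **Align the recording rules** in Protocol 7.1.1, 7.2.2.1 and 7.2.2.2 with that definition: enter a post-dose increase in frequency of a pre-dose AE as a new record with its own start date, and say so in the eCRF completion guidance.
3. **For the 11 subjects already randomized,** review every Screening-onset AE still open at first dose, and report any that worsened on drug with the TEAEs. Note the definition under SAP 19.

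Collection is over, so for this trial only the definition and the review can change the results; the recording rule serves later studies. The cost is a few sentences and a short listing review. The downside is that a few more TEAEs may be counted in every arm, including placebo. The stop rule needs no change for the planned analyses.
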